Using a suite of innovative methods, ours will be the first study to comprehensively assess the direct effects of exercise on features of WAT quality both in vivo (formation of new adipocytes and adipocyte TG turnover) and ex vivo (cellular landscape of WAT) and WAT-specific IR (suppression of lipolysis via subcutaneous microdialysis) in humans with obesity. Using a practical approach of isotopic labeling that incorporates deuterium (2H), administered as oral 2H2O, into the DNA and TG moieties of adipocytes, we have compelling published and preliminary evidence that exercise reduces in vivo formation of new adipocytes in both mice and humans, suggesting an important exercise-induced mechanism of WAT remodeling [3-5]. We reason that increased adipocyte TG turnover rates improve adipocyte function, WAT-specific IR and overall WAT quality and thus abrogate the need for increased formation of new adipocytes.

Adipocytes comprise 90% of the tissue volume, but only ~50% of WAT cellular content, with the remainder comprised of immune cells, stem cells, and pre-adipocytes [6, 7]. Using our established method [8], we will employ innovative single nuclei transcriptomics (snRNAseq) to discover the effects of exercise on senescence and inflammation within adipocytes and non-adipocytes of WAT to further understand how exercise impacts WAT quality and WAT-specific IR via in vivo microdialysis during insulin suppression.

Study Objectives

The overall aim of this study is to investigate the effects of exercise training on adipogenesis, TG turnover and cellular composition of adipose tissue, and insulin resistance in subjects with obesity.

Primary Objective/Aim/Goal/Hypothesis

The primary aim of this study is to investigate the effects of 12-weeks of endurance exercise training on *in vivo* formation of new adipocytes, TG turnover rates, and cellular composition of the WAT.

Approach: A subcutaneous WAT biopsy from the abdomen will be collected before and after 12 weeks of deuterium (2H) labelled water administration and endurance exercise training in men and pre-menopausal women with obesity. Collected WAT samples will be utilized for *in vivo* measurements of adipocyte formation and TG turnover. The remaining WAT samples will be frozen for future analyses that include snRNAseq and histology to assess cellular composition, senescence, and inflammation of the WAT

Secondary Objective/Aim/Goal/Hypothesis

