The TRI facility will be the main repository for biospecimen samples. PBRC will ship all tissue and blood samples (with exception of WAT samples needed for triglyceride turnover and adipocyte formation analysis and screening/safety visits) to AH TRI for testing and storage. The AH TRI will ship WAT samples needed for triglyceride turnover and adipocyte formation analysis. Material Transfer Agreements will be in place prior to transferring any samples between study sites. The MTA will govern the transfer and chain of custody of biospecimens outside of AdventHealth.

Current Version Date: 08/05/2024 IRBNet #: 1805407
Page 26 of 42

The adipose tissue specimens and plasma/serum samples will be stored indefinitely, or until a sample is fully used. All biological specimens will be stored without identifiers or linkage codes.

After study aims have been achieved and study related endpoints have been measured and analyzed, any remaining biospecimens will be stored at the TRI Laboratory Room 2404 and will then be considered as "archived biospecimens." Archived biospecimens will be used for any additional hypothesis-related experimentation or testing for the purposes of this study, consistent with the original aims, which cannot be predicted at the time the protocol is developed due to the evolving nature of scientific exploration.

Additionally, archived biospecimen samples may be stored indefinitely for future research. Archived biospecimens could be used for separate research by both
AdventHealth and PBRC scientists and scientists outside of AdventHealth and PBRC. This would be allowed for research of any type (without limitation to disease, process, or research methods) if it has scientific merit as determined by the PI, with an additional review by the respective Program Director. For research outside of AdventHealth or PBRC, a Material Transfer Agreement will be obtained, which will govern the transfer and chain of custody of the biospecimens outside of AdventHealth or PBRC.

Study Outcome Measures (Endpoints)

Primary outcomes:

- 1. In vivo adipogenesis in WAT. New adipocyte formation will be assessed two times (pre and post intervention) on the frozen isolated ²H₂O labelled adipose tissue cells.
- 2. In vivo TG turnover. WAT TG turnover rates will be assessed two times (pre and post intervention) on abdominal subcutaneous WAT on the extracted lipid from the frozen ²H₂O labelled adipose tissue.

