The primary aim is powered to detect differences in the change in *in vivo* formation of new adipocytes (i.e., fraction of newly formed adipocytes; "f") of subcutaneous WAT between the CTRL and EX groups. We hypothesize that the EX-group will have a decrease in the fraction of newly formed adipocytes in response to the EX intervention as compared to the CTRL group. Analysis of women from our previous VIVA study (NCT03530111) indicates that the mean value of "f" in the physically active (exercise) group is 11.4%, while the sedentary group has an "f" value of 17.8%. Because VIVA only has crosssectional data (assessment at one time-point), we must also use data from the Apple & Pear study (NCT01748994) 9 to estimate the change in fraction of newly formed adipocytes, as the proposed study includes an exercise intervention. By utilizing data from the CTRLgroup in the Apple & Pear study 9 (baseline assessment) and increasing the estimate to ensure that the study is well-powered, we can estimate the CTRL and EX groups from the proposed study to have an overall mean "f" value of 17% (at baseline) with a standard deviation of 6.0%. A total sample size of 58 (assuming a ~17% overall lost-to-follow-up rate) will provide at least 80% power to detect significant differences in "f" between the CTRL and EX groups, with a 5% significance level.

Current Version Date: 08/05/2024 IRBNet #: 1805407
Page 29 of 42

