Single nuclei RNAseq Power Calculation. To date the most comprehensive analysis of human WAT has been conducted by Emont and colleagues who performed snRNAseq in whole frozen WAT and VAT from humans with obesity and established 17 subpopulations of cells. However, these data were generated using the 10X Genomics platform. We have published preliminary snRNAseq data in WAT from 22 individuals with overweight and obesity. We expect to capture nuclei from the WAT that may reveal up to 12 different cell populations (Fig. 4). If we assume the rarest cell type is 2% and require at least a 100 of the of rarest cell type to accurately quantify and describe it, we require a total of 6,792 nuclei to achieve a 99% probability of meeting these requirements. Our current technique permits 1400 cells per participant to be analyzed which equates to 28,000 cells for 20 participants at each timepoint in EX-group and 14,000 nuclei for 10 participants at each timepoint in the CTRL-group. This would allow us to accurately define subpopulations within WAT and generate sufficient data to compare the impact of endurance exercise on adipocyte populations and non-adipocyte populations.

Statistical Analysis Plan

Primary and Secondary Objective Analysis

Shapiro-Wilk test will be initially performed to assess the normality of data and homogeneity of variances. Pre- and post-intervention results will then be tested by paired t-test or Wilcoxon signed-rank test, as appropriate. Results will be expressed as mean \pm standard deviation and significance will be established, *a priori*, at p≤0.05.

Potential Risks and Benefits

Potential Benefits

The potential benefits to an individual participant in this study are not known. Exercise training can trigger many beneficial adaptations, but individual responses and adaptations vary. All participants will acquire knowledge about their physiological status (e.g., cardiorespiratory fitness, body composition, etc.) that may be of personal benefit. The risks presented to participants are minimal, and information gained from this project will be useful to identify mechanisms responsible for exercise effects on adipose tissue quality and insulin resistance in subjects with obesity.

Potential Risks

Described below are all the known risks of being in this study.

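### New-adipocyte fraction and TG turnover are defined as pre and post measures, but the pre biopsy precedes all labelled water, so neither has a baseline value or a within-person change

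*Protocol*

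**What the plan says.** **Method.** The Background section says the labelling approach "incorporates deuterium (2H), administered as oral 2H2O, into the DNA and TG moieties of adipocytes". New-cell formation and TG turnover are both inferred from that label.

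**Outcomes.** Under Study Outcome Measures (Endpoints), primary outcome 1 reads "New adipocyte formation will be assessed two times (pre and post intervention) on the frozen isolated" labelled cells. Primary outcome 2 reads "WAT TG turnover rates will be assessed two times (pre and post intervention) on abdominal subcutaneous WAT", again on labelled tissue.

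**Sample size.** The section opens "The primary aim is powered to detect differences in the change in" new adipocyte formation. It takes a mean f "value of 17% (at baseline) with a standard deviation of 6.0"%. It cites a previous cross-sectional study of women, in which mean f "in the physically active (exercise) group is 11.4%, while the sedentary group has an" f of 17.8%. It concludes that 58 participants "will provide at least 80% power to detect significant differences in" f between CTRL and EX.

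**Analysis.** The Statistical Analysis Plan section of the protocol says "Pre- and post-intervention results will then be tested by paired t-test or Wilcoxon signed-rank test, as appropriate". It names no between-group test.

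**Schedule.** The pre biopsy is on the morning of Day -7 (Baseline Visit 2). The first labelled water is collected afterwards, at the visit where the biopsy site is checked. It is drunk in Weeks 1 to 12, and the second biopsy is on Day 88.

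**The concern.** A measure that depends on incorporated label needs a labelling period before the biopsy. The Day -7 biopsy has none. A pre value of f or of TG turnover therefore cannot exist, and neither can a change from it. The powered endpoint is such a change, and the only test named for pre and post results is a paired one.

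If that test were run on these two outcomes, its null hypothesis would be that labelled tissue carries no more label than unlabelled tissue. That null is false in both arms whatever exercise does. A report could then show a highly significant change in f in each arm, neither of them evidence about training.

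**Working it through.** **1. Timeline (visit sections and the two schedule tables in the Appendix)**

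| Event | Day | Window |
|---|---|---|
| Visit 1 | -14 | ±2 |
| Pre WAT biopsy | -7 (visit starts Day -8) | ±2 |
| Labelled water, Weeks 1-12 | 0 to 83 | ±1 per week |
| Post WAT biopsy | 88 | ±2 (visit text) |

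At the extremes of the windows, the latest pre biopsy is about Day -7 + 2 = -5 and the earliest labelled water about Day 0 - 1 = -1. The order cannot reverse. Neither schedule table shows labelled water before Week 1. Visit 1 to Day 88 is 102 days, or 102/7 = 14.6 weeks, in line with the stated participation of about 14 weeks, so there is no room for an earlier labelling period.

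**2. What each biopsy can give**

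- Day -7: natural background enrichment only.
- Day 88: label accumulated over 12 weeks, giving one f and one TG turnover rate per person.
- Primary outcomes 3 and 4 (cell composition; morphology, senescence, inflammation) and the clamp and microdialysis outcomes need no label. Pre and post values exist for them.

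**3. The protocol's own figure**

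Inputs: SD 6.0; 58 completers at 1:1, so 29 per arm; 5% level, two-sided assumed. The only difference given is 17.8 - 11.4 = 6.4 points, which is not expressly named as the design difference. All power figures use the exact two-sample t-test.

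For a change score, SD of change = 6.0 × √[2(1 - ρ)]. With ρ = 0 (assumed; no correlation is stated) this is 6.0 × √2 = 8.49. The required n for 80% power at 6.4 points is 28.6, so 29 per arm or 58 in total, with power 80.6%. The figure of 58 is therefore compatible with sizing on a change in f, although the protocol does not state this derivation. Enrolment agrees: 58/(1 - 0.17) = 69.9, so 70.

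**4. The comparison the schedule supports**

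One post-labelling f per person, EX versus CTRL, 29 per arm. The standard error of the difference is 6.0 × √(2/29) = 1.58 points, and 6.4/1.58 = 4.06.

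| SD of f after labelling | Power for 6.4 points | Difference with 80% power |
|---|---|---|
| 5 (assumed) | 99.8% | 3.74 |
| 6.0 (protocol) | 97.9% | 4.49 |
| 7 (assumed) | 92.8% | 5.24 |
| 8 (assumed) | 84.9% | 5.99 |

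At SD 6.0, smaller assumed differences of 5, 4 and 3 points give power of 88%, 70% and 46%.

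**5. What the paired test would do**

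Take a control arm with f 17%, SD 6, no exercise effect, and a pre value near zero because there is no label. The paired t statistic is about 17/(6/√29) = 15.3. In 4,000 simulated control arms of 29, with background noise of SD 0.5 points (assumed), the paired test rejected in 100%. A two-sample comparison of post values with no true effect rejected in 4.4%.

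**The case against.** The strongest reply is that the design is sound and only its description is loose. Assessing formation twice may mean assaying both biopsies with the first as background. The sample size section states its hypothesis as EX compared with CTRL and ends on a between-group difference in f. The analysis paragraph is short and generic, does not name f, and a separate SAP may specify the model.

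Much of this is fair. The protocol gives no formula for f, so calling the Day -7 sample background only is an inference from the labelling method. The between-group intent is visible. But the background reading does not rescue a 17% f at baseline, or a change in f. Nor is this a detail left to a SAP: the protocol itself fixes the endpoint, the powered quantity and the test, and its schedule cannot supply the first two.

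A second reply concerns power. The 6.4-point gap is cross-sectional, from women only, between active and sedentary groups; the trial trains sedentary men and women for 12 weeks. That stands. The 98% figure is conditional on 6.4 points being the design difference, and 58 participants are enough only for differences of about 4.5 points or more at SD 6.0. The change-score reconstruction shows compatibility, not how 58 was derived.

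Third, a within-arm paired test leaves the randomised control unused for the other outcomes too. That is true but separate: for those outcomes the pre value at least exists.

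**Conclusion.** The concern holds. As written, primary outcomes 1 and 2 have no obtainable pre value, the powered change in f cannot be computed, and the only named test would be uninformative about exercise for both. This affects two of the four primary outcomes, including the one that sets the sample size.

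The trial itself is not undermined. The Day 88 biopsy carries a valid randomised comparison, with 80% power for about 4.5 points at 29 per arm. This rests on SD 6.0 applying to f after 12 weeks of labelling and on a two-sided 5% level. If the SD is between 5 and 8, the detectable difference runs from 3.7 to 6.0 points. The timeline finding rests on no assumed number. The text must be corrected before data are analysed.

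**What to change.** - **Study Outcome Measures, primary outcomes 1 and 2.** Define them as f and TG turnover accrued over the 12-week labelling period, measured in the Day 88 biopsy, with the Day -7 biopsy supplying background enrichment only. Leave outcomes 3 and 4 as pre and post measures.
- **Statistical Analysis Plan section.** Make the primary analysis of these two outcomes a between-group comparison, EX versus CTRL, in place of the paired test.
- **Sample Size Determination.** Remove the references to a change in f and to a baseline mean. Name the design difference and justify it. Restate power for a single post-labelling f: 29 completers per arm, SD 6.0 and two-sided 5% give 80% power for about 4.5 points, and about 98% for 6.4 points if that is the difference chosen. If the sponsor considers a difference below about 4.5 points realistic, the sample size needs to be revisited.

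The cost is wording in three sections. No biopsy, labelling period or participant is added. The claim of a within-person change in f and TG turnover is given up, but the schedule never allowed it.

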- 3. Cellular composition of WAT. Cell composition and gene expressions in WAT will be assessed two times (pre and post exercise intervention) by snRNAseq on the frozen adipose tissue.
- 4. Adipocyte morphology, senescence, and inflammation. Adipocyte size, markers of cellular senescence and inflammation will be assessed two times (pre and post exercise intervention) by immunohistochemistry on the formalin-fixed paraffin-embedded adipose tissue.

Secondary outcomes:

1. Whole body and WAT-specific insulin resistance: Whole-body insulin resistance and WAT-specific antilipolytic sensitivity to insulin will be evaluated pre and post exercise intervention *in vivo* using blood and dialysate samples collected during glucose clamp and subcutaneous microdialysis.

Data Management and Quality Plan

Data De-identification

Participants will be enrolled and assigned a participant identification number (PID). This PID is a code consisting of a combination of numerals and letters, which serves as the identifier for this participant for this research study and links them back to their hospital medical record and their protected health information (PHI). Access to the "link" between the PIDs, the PHI, and to the clinical data are only granted to the clinical research team as assigned on the Delegation of Authority Log. All the clinical research and survey data is recorded in a de-identified fashion onto our paper source documents and/or electronic case report forms (CRF). Both sites will enter data into REDCap, a HIPAA-compliant, web-based forms and survey platform approved for use by AdventHealth. REDCap will be used for storage and to facilitate analysis. All data not entered into REDCap (e.g., data collected from individual exercise sessions) will be stored on a shared OneDrive folder only accessible to the assigned study-specific research team at PBRC and AH TRI.

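### Four primary outcomes share one p≤0.05 threshold with no lead outcome or test order, although only f is powered for a group comparison

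*Protocol*

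**What the plan says.** The section Study Outcome Measures (Endpoints) of the protocol lists four outcomes as primary:

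1. Adipogenesis: "New adipocyte formation will be assessed two times (pre and post intervention").
2. TG turnover: "WAT TG turnover rates will be assessed two times (pre and post intervention").
3. The snRNAseq outcome: "Cell composition and gene expressions in WAT will be assessed two times (pre and post exercise intervention) by snRNAseq on the frozen adipose tissue". It covers both cell composition and gene expression and gives no list of genes or cell types.
4. Histology: "Adipocyte size, markers of cellular senescence and inflammation will be assessed two times (pre and post exercise intervention) by immunohistochemistry".

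The Statistical Analysis Plan section has one short paragraph for primary and secondary objectives together. On the test it says "Pre- and post-intervention results will then be tested by paired t-test or Wilcoxon signed-rank test, as appropriate". On the threshold it says "significance will be established, *a priori*, at p≤0.05". It gives no lead outcome, test order, adjustment or false discovery rate.

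Sample Size Determination bases the power of the primary aim on the change in f between control and exercise, "with a 5% significance level". It then gives a separate snRNAseq calculation, which finds how many nuclei are needed to describe a rare cell type.

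**The concern.** Each of the four outcomes carries the label primary, and each is to be judged at the full 5%. The trial was sized for one of them. If f shows nothing and one of the other three falls below 0.05, the protocol gives no basis for saying whether the primary aim has been met. The 5% error rate then applies to each test and not to the claim that exercise changes a primary feature of adipose tissue. Outcomes 3 and 4 add to this because each holds several measures, and no one of them is named as the measure to be tested.

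**Working it through.** **Inputs from the protocol.** Four primary outcomes and p≤0.05 for all of them. For f: means of 11.4% (active) and 17.8% (sedentary), SD 6.0%, total N 58, about 17% loss to follow-up, 70 enrolled, 1:1 allocation. For snRNAseq: up to 12 cell populations.

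**Assumptions.** Tests are two-sided. The pre-post correlation ρ of f is not given. Correlations between outcomes are not given, so a range is shown. There is one between-group test per outcome, because that is the contrast the sample size uses.

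**Step 1: reproduce N = 58.** The protocol states no target difference in change, so the difference between the two group means is used: 17.8 − 11.4 = 6.4.

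- SD of change = 6.0 × √(2(1 − ρ)). At ρ = 0 this is 8.49, so the standardised effect is 6.4 / 8.49 = 0.754.
- A two-sample t-test with 29 per arm at α = 0.05 has 80.6% power.
- If 6.0 is itself the SD of change (ρ = 0.5), power is 97.9%. Both values meet the stated 80%.
- Enrolment: 58 / (1 − 0.17) = 69.9, rounded up to 70.

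The planned size is therefore that of a single test of f at 5%.

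**Step 2: what the snRNAseq calculation covers.** It asks for 6,792 nuclei, to be 99% sure of at least 100 nuclei from a cell type making up 2%. It contains no effect size, significance level or group comparison, so it does not power a treatment contrast.

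**Step 3: chance of at least one false primary result when there is no true effect.** For k independent tests this is 1 − 0.95^k.

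| Tests counted | k | Independent |
|---|---|---|
| The three outcomes other than f | 3 | 14.3% |
| One test per primary outcome | 4 | 18.5% |
| Seven named measures (f, TG turnover, composition, expression, cell size, senescence, inflammation) | 7 | 30.2% |
| Cell populations alone, if all 12 are found and tested | 12 | 46.0% |

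Simulation of four equally correlated tests (400,000 replicates) gives 17.4%, 15.5% and 11.4% at correlations of 0.3, 0.5 and 0.8. For two-sided tests with jointly normal statistics, independence gives the largest value for a given k, so the table shows ceilings.

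The protocol does not say how many genes would be tested. Every 1,000 genes with no true effect would give 1,000 × 0.05 = 50 false positives on average at an unadjusted 0.05.

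**Step 4: two ways to restore 5%.**

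- f as sole confirmatory outcome: error 5%, N stays at 58 completers and 70 enrolled.
- Bonferroni over four outcomes, one pre-named measure each, at 0.05 / 4 = 0.0125. Power for f with 29 per arm falls from 80.6% to 61.6% (SD of change 8.49). Restoring 80% takes 41 per arm, which is 82 completers and 82 / 0.83 = 98.8, so 99 enrolled. If 6.0 is the SD of change, power at 0.0125 is still 92.6%.

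**The case against.** **This could be left to a separate SAP.** Multiplicity control often is, one may exist here, and the protocol never says its p-values are unadjusted. It is true that a later SAP could add error control. But the protocol has its own analysis section, which fixes the threshold in advance for all primary and secondary objectives. The point concerns that stated rule.

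**No success rule is written.** A reader might infer that any one significant test establishes the primary aim. The text does not say so. What stands is that four outcomes are called primary and nothing ranks them.

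**A false primary result might be called likely.** The figures of 18.5% and 30.2% do not support that word, and the outcomes come from the same biopsies, so positive correlation is plausible. A reader might reach 51.2% by counting seven paired tests in each of two arms (1 − 0.95^14). That count fails for three reasons:

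- A pre-post change in controls is not a claim about exercise.
- The analysis section does not say that the paired tests are run by arm.
- The baseline biopsy precedes the first labelled water, so a 5% pre-post null does not describe f or TG turnover.

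**Transcriptome-wide testing at 0.05 might be inferred.** The protocol names gene expression by snRNAseq but specifies no gene-level test and no gene count. Under the primary aim it also describes snRNAseq and histology as future analyses of frozen tissue. That weakens any numerical claim about genes, and it supports an exploratory label.

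**The protocol has a power calculation for snRNAseq.** It does by heading, but Step 2 shows that it concerns capture of nuclei.

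**Several primary outcomes can be legitimate.** They can, if the protocol says how each is to be interpreted or splits the error rate. This one does neither, and Step 4 shows that splitting may cost a good deal of power for f.

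**Conclusion.** The point holds. The protocol names four primary outcomes, applies p≤0.05 to each and powers only f for a group comparison. With one between-group test per outcome, the chance of at least one false primary result is 18.5% if independent, about 3.7 times the nominal 5%, and 11.4% to 17.4% at correlations of 0.8 to 0.3. It is 30.2% for the seven named measures if independent. It rises further if cell populations or genes are tested singly at 0.05, by an amount that cannot be fixed because the number of genes is not stated.

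These figures assume two-sided tests, no true effect on any outcome, and no error control in a separate SAP. They do not show that a false primary result is likely. They show that the stated rule does not hold the primary error rate at 5% and leaves open which result decides the trial.

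**What to change.** - In Study Outcome Measures, name the between-group difference in f as the single confirmatory primary outcome, tested at two-sided 5%.
- Make TG turnover the key secondary outcome, tested only if f is significant. This fixed order keeps the error rate over the two tests at 5%.
- Label cell composition, gene expression, histology, senescence and inflammation secondary or exploratory.
- In the Statistical Analysis Plan section, limit the p≤0.05 rule to f and the ordered key secondary, and state false discovery rate control for snRNAseq cell-type and gene tests.
- Adjust the wording of the primary aim under Study Objectives, which now puts adipocyte formation, TG turnover and cellular composition side by side.

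The cost is relabelling, a light rewording of the aim and one sentence on test order. Fewer results can be called primary. No assay is dropped, and the sample size stays at 58 completers and 70 enrolled.

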The secondary aim of this study is to assess the effects of 12-weeks of endurance exercise training on WAT-specific IR and fasting FFA levels and molecular adaptations in skeletal muscle that may contribute to the alterations in WAT.

Approach: Blood samples and dialysates from abdominal subcutaneous WAT will be collected during hyperinsulinemic clamp to assess whole-body IR and WAT-specific suppression of lipolytic rates under physiological insulin in men and pre-menopausal women with obesity. A skeletal muscle biopsy from the vastus lateralis will be collected before and after 12 weeks of deuterium (2H) labelled water administration and endurance exercise training to assess transcriptomic and proteomic adaptation that may associate with WAT adaptations.

Study Design

Research Design

This is a double-site (AH TRI and PBRC), longitudinal (12 weeks) randomized clinical trial with two groups; a control group (CTRL) and an exercise training group (EX)

Research Intervention Description

Subjects will be submitted to 12 weeks of supervised aerobic exercise training intervention and oral deuterium-labelled water administration OR oral deuterium-labelled water administration only.

This study consists of a Screening Period, Baseline Period, Intervention Period, and Follow-up Period, detailed below.

Study Site(s)/Location(s) and Number of Subjects

AdventHealth Orlando Sites: Translational Research Institute (TRI)

Estimated number of subjects at AdventHealth Orlando site: 35 men and women (accounting for a 20% dropout; we expect 29 to complete the study)

Name of external site(s) outside of AdventHealth Orlando: Pennington Biomedical Research Center

Estimated number of subjects at external sites: 35 men and women (accounting for a 20% dropout; we expect 29 to complete the study)

Total number of all sites: 2

Estimated number of subjects at all sites combined: 70

Multi-Site Research Logistics/Communication Plan

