Waiver or Alteration of the Consent Process (consent will not be obtained, required information will not be disclosed, or the research involves deception)

N/A

Waiver or Alteration of HIPAA Authorization

Partial waiver of HIPAA authorization will be requested.

Non-English Speaking Subjects

We intend to enroll only English-speaking participants due to the complexity of the study procedures and the lack of translational capacity that could be adequately provided throughout the duration of the study.

Randomization

Men and women will be randomized to the CTRL and EX groups on a 1:1 basis following successful completion of the VO₂max test and imaging tests. Participants will be stratified by sex to ensure balance between each of the groups. Stratifying allows for different sample sizes in each sex, but ensures that within each sex, there are an equal number of treatments and controls.

Study Visits

Study visits will be conducted at the AdventHealth Translational Research Institute or Pennington Biomedical Research Center.

Screening Visit (SV) (Outpatient; Approximate visit time: 2 hours)

Participants will arrive for this outpatient visit after a 10 hour overnight fast. After obtaining informed consent, data collection for assessing eligibility will commence. The screening visit will include:

¹Urine for pregnancy test (if applicable), urinalysis, and toxicology screen (Amphetamine, Barbiturate, Benzodiazepine, Cocaine, Methadone, Opiate, THC, Cannabis, Tricyclics, and Oxycodone)

²Demographics and complete medical history (including, but not limited to, alcohol use, concomitant medications, health conditions, allergies and exercise habits)

³Vital signs (respiratory rate, temperature, heart rate, blood pressure)

⁴Standard physical examination performed by a study physician, physician assistant, or nurse practitioner

⁵Anthropometrics including height, weight, waist circumference, and BMI

⁶Screening blood draw to measure CBC with differential and platelets, comprehensive metabolic panel (CMP), lipid profile, blood glucose, HbA1C, ALT, AST, alkaline phosphatase, insulin level, and TSH

⁷Electrocardiogram (ECG)

⁸Consent Process Checklist assessing the potential participants' understanding of and willingness to perform all study activities.

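### The analysis section gives Shapiro-Wilk a variance check that it cannot make, lets the data choose between two paired tests, and names no EX versus CTRL comparison, although the trial is powered on one

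*Protocol*

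**What the plan says.** Protocol, Statistical Analysis Plan, Primary and Secondary Objective Analysis, is three sentences long.

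- First: "Shapiro-Wilk test will be initially performed to assess the normality of data and homogeneity of variances".
- Then: "Pre- and post-intervention results will then be tested by paired t-test or Wilcoxon signed-rank test, as appropriate".
- Last: "Results will be expressed as mean" with standard deviation, and "significance will be established, *a priori*, at p≤0.05".

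The section names no test, estimate or interval that compares the two groups.

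Elsewhere the protocol describes a parallel-group comparison. Under Randomization: "Men and women will be randomized to the CTRL and EX groups on a 1:1 basis", stratified by sex. Under Sample Size Determination: "The primary aim is powered to detect differences in the change in *in vivo* formation of new adipocytes" between CTRL and EX, with 58 participants, at least 80% power and a 5% significance level.

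**The concern.** Three things look wrong.

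1. **Wrong tool.** Shapiro-Wilk carries no information about whether two variances are equal, so the stated variance check would not be made. Nor is that check relevant to the tests that follow: a paired t-test and a signed-rank test both work on within-person differences and do not assume equal variances across arms.
2. **Data-driven test choice.** The test follows from a look at the data. The text does not say whether the check is on raw values or on differences (the paired t-test concerns differences), what cut-off applies, or whether the choice is made per arm or once per outcome. A signed-rank p-value could sit beside a mean and SD that it does not test.
3. **No between-arm analysis.** A paired pre/post test answers whether an arm changed, not whether EX changed more than CTRL. Followed as written, the section yields no estimate of the effect on which the trial is powered.

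The third carries most of the weight.

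**Working it through.** **1. What the plan is powered for.** Inputs from Sample Size Determination: *f* of 17.8% (sedentary) and 11.4% (active), SD 6.0 points, total 58, loss about 17%. Two-sided 5% is assumed because sidedness is not stated.

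- Difference: 17.8 − 11.4 = 6.4 points.
- SD of change: 6.0 × √(2(1 − ρ)). With ρ = 0 (assumed), this is 6.0 × √2 = 8.49.
- n per arm = 2 × (1.960 + 0.842)² × (8.49/6.4)² = 2 × 7.85 × 1.758 ≈ 27.6, so 28 by the normal approximation. The t-based version gives 29, hence 58 in total.
- Inflation: 58 / (1 − 0.17) = 69.9, so 70, as stated.
- Power at 29 per arm: SE = 8.49 × √(2/29) = 2.23; 6.4/2.23 − 1.96 = 0.91; power 81.9% (normal), 80.6% (t).

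The figure of 58 thus reproduces as a two-sample comparison of change. The protocol does not state the 6.4-point target or ρ = 0 as its inputs. With SD 6.0 used directly (the same as ρ = 0.5), 14 to 15 per arm would suffice, and power at 29 per arm would be about 98%.

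**2. Can Shapiro-Wilk detect unequal variances?** Simulated normal data, 29 per arm, tests at 0.05:

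| SD ratio between arms | Shapiro-Wilk rejects, within each arm | Shapiro-Wilk rejects, arms pooled | Levene rejects |
|---|---|---|---|
| 1 | about 5% | 5% | 5% |
| 2 | about 5% | 24% | 88% |
| 3 | about 5% | 58% | 99.7% |

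Within an arm it does not react at all. The pooled rate rises only because a mixture of two normals is not normal.

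**3. How often would the arms get different tests?** Assume the check is run separately in each arm at 0.05. If it rejects with probability *p* in each arm, the choices differ with probability 2*p*(1 − *p*).

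- Normal differences: *p* = 0.054, so 2 × 0.054 × 0.946 = 10%.
- t with 5 df: *p* = 0.248, so 2 × 0.248 × 0.752 = 37%.
- Log-normal values: the protocol's mean of 17% and SD of 6.0% give a CV of 6/17 = 0.353 and a log SD of √ln(1 + 0.353²) = 0.34, so 0.35 is a fair assumption. For pre/post differences of such values with no shift in mean, the arms differ in about 24 to 25% of trials at correlation 0, 27 to 28% at 0.5 and 29 to 30% at 0.8 (ranges over repeated simulations).

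**4. Does the gate damage type I error?** One-sample error of the gated procedure against a fixed t-test, 29 participants:

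- normal differences: 5.3% against 5.3%;
- t with 5 df: 5.0% against 4.9%;
- differences of log-normal values: 5.6% against 5.3%;
- differences that are themselves strongly skewed: about 7.9% against 5.6 to 6.1%.

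**The case against.** The best defence is that the variance phrase is a slip without consequence. Neither named test needs equal variances, so striking the words changes no named analysis. Two-stage test choice is common, and step 4 shows that it usually does little harm. When differences are roughly symmetric, the two tests address the same centre. The cut-off and the per-arm application are inferred, and the wording leaves room for one choice per outcome. Such details are often left to a statistical analysis plan, which may exist and is not at hand.

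Most of this stands and limits the point. Three stronger readings that a reader might infer are not supported:

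- **That the arms would be split between tests in about half of trials.** A figure near 49% arises only when raw log-normal values are fed to the check. For differences, on which the paired t-test depends, it is about 25 to 29%.
- **That the gate seriously inflates false positives.** It does so only when the differences themselves are strongly skewed, which nothing in the protocol shows.
- **That the gate is why there is no between-arm estimate.** That gap comes from naming only pre/post tests. Removing Shapiro-Wilk alone would leave it open.

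The defence does not reach the section's own content. It describes the analysis of the primary and secondary objectives and gives tests that do not address the powered comparison. A separate plan could add detail, but it should not have to overrule the protocol.

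**Conclusion.** The point holds in a limited form. The statement about homogeneity of variances is wrong but has almost no effect on the tests named. The data-driven choice is a modest weakness. If applied per arm at 0.05, it would give the arms different tests in about 10% of trials with normal differences and about 25 to 29% under the log-normal assumption, with little effect on type I error in most settings. All the non-normal scenarios are assumptions, because the protocol gives only a mean and an SD for *f*.

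The defect that matters is that the section names no EX versus CTRL analysis in a 1:1 randomised trial whose sample size concerns that difference. This does not show that no such comparison will ever be made, only that the protocol's stated analysis does not contain it. The sample size is not at fault: under the assumptions that reproduce 58, a two-sample comparison has about 80.6% power.

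**What to change.** In Primary and Secondary Objective Analysis:

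- Delete the reference to homogeneity of variances and the Shapiro-Wilk step as a rule for choosing the test.
- Make one pre-specified linear model per outcome, EX versus CTRL, the primary analysis. Adjust for sex (the stratification factor), site, and the baseline value where one exists. That qualifier matters for *f* and triglyceride turnover, because the schedule places the first adipose biopsy at Day −7, before labelled water starts in Week 1.
- Fix the scale of each outcome in advance (for example, log for skewed fractions), and use standard errors that allow unequal variances. No preliminary variance test is then needed.
- Report the between-arm difference with its 95% CI.
- Keep within-arm pre/post tests and a rank-based test as supportive analyses only.

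Other models would also serve. What matters is that the comparison is between arms and chosen before the data are seen. The cost is a few lines of wording and no extra participants.
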